8.8 KNOWN POTENTIAL BENEFITS

The possible benefits of participation are as follows:

- Subjects and their parent/guardian who return for neurodevelopmental evaluation will learn about those aspects of the proband's neurodevelopmental status that are assessed by the battery of tests. Findings will be summarized in a formal written report, with the opportunity for subjects to discuss findings with the center Investigator(s). If the subject/parent/guardian provides consent, this information will also be shared with the primary caregiver and/or cardiologist.
- If there are areas in which a subject is functioning poorly or if neurological problems are discovered, these can be identified and recommendations for further evaluation or intervention provided, as appropriate.
- We offer an option for subjects to learn, at the end of the study, whether they/their children carry pathogenic genetic variants that are likely to have caused their congenital heart disease and/or affected their development and behavior. Although subjects with pathogenic mutations in previously known CHD genes will have been excluded from this protocol at study onset, we expect that we will have discovered new pathogenic mutations by the end of the study period. All disclosure of genetic results at the end of the CHD Brain and Genes Study will be guided by the PCGC's Disclosure of Results Committee, chaired by renowned geneticists Drs. [name] and [name].
- To ascertain whether the research tests result might be relevant to subjects, they must first be confirmed in a CLIA-approved laboratory using new blood and/or saliva samples. If participants choose to receive their genetic results and have a pathogenic mutation, they will have the opportunity to speak with geneticists or genetics counselors about the results. The costs of the additional blood test and genetic counseling will be paid for by this research study and will not be charged to study participants.

- In most cases, knowing the results of DNA analysis done as part of PCGC1 will not provide direct benefit to individual subjects or families. The benefits are those to society as a whole in the improvement of knowledge of the genetic causes of CHD and of NDD, in the development of new diagnostic tests and ultimately in the improvement of treatment and prognosis.
- An indirect benefit may also come from the awareness that the results of this study may serve to help improve the care of patients with similar neurodevelopmental challenges in the future. CHD patients and their families may derive a sense of altruism, accomplishment, and contribution to furthering understanding of neurodevelopmental outcomes in individuals with congenital heart disease through their participation

The research examining the association of DNA results, neurodevelopmental performance, and brain MRI may result in inventions or discoveries that could create new tests and medicines that have commercial value. Although subjects and/or their parent/guardian will not receive compensation now or in the future for use of their data, income that may be derived from future research or sales of the grouped data may be used to support biomedical research.

9 CLINICAL MONITORING

Clinical site monitoring is conducted to ensure that the rights and well-being of human subjects are protected, that the reported trial data are accurate, complete, and verifiable, and that the conduct of the trial is in compliance with the currently approved protocol/amendment(s), with GCP, and with applicable regulatory requirements. Risk-based monitoring will be utilized for this trial. Details of clinical site monitoring are documented in the Clinical Monitoring Plan (CMP).

10 STATISTICAL CONSIDERATIONS

10.1 STATISTICAL HYPOTHESES

We hypothesize that patients with deleterious mutations will have more neurodevelopmental abnormalities than CHD patients without these mutations. In exploratory analyses with limited statistical power, we expect to see the greatest developmental deficits in subjects with deleterious mutations in loss of function genes that are expressed in both the heart and brain. We also hypothesize that there will be worse outcomes in patients with independent deleterious mutations in heart and brain, as well as in those with either deleterious mutations or unfavorable polymorphisms in neuroresilience genes.

10.2 DESCRIPTION OF STATISTICAL METHODS

10.2.1 GENERAL APPROACH

Patients will be classified into one of two groups: 1) patients with deleterious mutations and 2) patients without deleterious mutations. Although cases and controls will be chosen based upon available information at the study onset, the final classification will be performed at the conclusion of the study

and prior to data base lock and will be based on the current state of the science at that time by the genetic protocol team.

Demographic and clinical characteristics will be summarized for each of the two groups using mean, standard deviation, median, and interquartile range for continuous variables and frequency and percent for categorical variables. Statistical comparisons between the two groups will be performed using the two-independent sample t-test or the Wilcoxon rank sum test for continuous variables and the chi-square test or Fisher's Exact test for categorical variables. All tests will be performed at the two-sided 5% level of significance.

Neurodevelopmental Outcomes:

The primary neurodevelopmental study outcome is the WRAT-4 composite score, which has a mean of 100 and SD 15. Secondary outcomes include composite scores from each of the following 5 domains: Visual Spatial Skill, Intelligence, Memory, Executive Function, Language, Tests for Autism, Social Cognition, parent and teacher reported instruments.

The primary analysis for all endpoints (primary and secondary) will compare patients with and without known deleterious mutations and will include the matching factors of site, CHD type, sex, and age category using a generalized analysis of variance model. Because socioeconomic status (SES) has a proven effect on neurodevelopmental performance in virtually all published studies, we will also adjust for this variable in all models. An appropriate link and distribution function will be used depending on the distribution of the outcome variable (e.g. identity link and normal distribution for normal data, logit link and binomial distribution for dichotomous data). If assumptions of the model are violated, appropriate transformations will be performed (e.g. log, square root, rank) in order to satisfy the assumptions. Models supporting the primary analysis will include variables that may be associated with adverse neurodevelopment as covariates, (e.g., maternal education, history of prematurity or early term birth, number of open heart surgeries, number of cardiac catheterizations, number of serious adverse events, etc.). We will perform separate analyses for each potential covariate that include the variable, along with the matching factors and SES, and consider those variables associated with endpoint at a p -value <0.1 as covariates in stepwise generalized linear models. Collinearity will be assessed. The primary analyses and all secondary analyses will be conducted at the two-sided 5% level of significance. No multiple testing adjustments will be used for the secondary outcomes, although it is recognized that results of these tests should be interpreted with caution. Exploratory analyses of effect modification by neuro-resiliency polymorphisms may be performed by including interaction terms in the models.

MRI Outcomes:

MRI outcomes will include measures based on voxel-level analyses (e.g. grey matter volumes, regional cortical thickness, etc.) and outcomes that are summarized at the patient level (e.g. mean global FA). For unadjusted voxel-level analyses, two-sample t-tests (with appropriate transformations, if needed to satisfy the assumptions of the analyses) or Wilcoxon Ranks sum tests will be conducted to identify voxels that are significantly different between the two groups. P-value adjustments for multiple testing will be done to control the false discovery rate at 5% for voxel-level analyses for each MRI measure.

Using clinical and demographic variables that are differentially distributed between the two groups (as identified by $p < 0.10$ in univariate analyses) as potential covariates, adjusted analysis at the voxel level will be conducted using stepwise generalized linear modeling with appropriate distribution and link functions.

Unadjusted comparisons of MRI outcomes measured at the patient level for the two groups will be made using the two-sample t-test or Wilcoxon Rank Sum test. Additional analyses for patient level MRI outcomes will include adjustment for matching factors (site, sex, CHD type and age category) and other demographic and clinical characteristics that are differentially distributed between groups (as identified by $p < 0.10$ in univariate analyses) using stepwise regression models. Collinearity will be assessed and transformations used, if required, to satisfy the assumptions of the analyses. All tests will be conducted at the two-sided, 5% level of significance and no adjustment will be made for multiple testing for the MRI outcomes measured at the patient level.

Alternative approaches for analyzing the MRI and genetic data to determine if there is a significant association between genetic variants and brain MRI endophenotype in patients with CHD will be based on the state of the art statistical approaches that are available when the data base for this protocol is closed. The statistical analysis of MRI and genetic data is a rapidly evolving field and it is expected that more sensitive statistical approaches will be developed during the course of this study.

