2.2 RATIONALE

Neurodevelopmental disabilities (NDD) remain the most common sequelae of CHD, causing problems in school function, behavior, employability, and quality of life. Earlier prospective studies suggest that preoperative, intraoperative, and postoperative factors together can explain only one third of the variance in neurodevelopmental (ND) outcomes, suggesting an important role for as-yet-undescribed genetic factors. In this protocol, we will explore the association between genetic variants, neurodevelopmental deficits, and brain MRI endophenotype. Analyses will compare groups with and without deleterious de novo mutations or stringently-defined missense mutations by meta-SVM, frequency matched for type of CHD, age group, and sex. We will exclude subjects with copy number variants (CNVs) deemed to be known clinically pathogenic (e.g. 22q11) from both groups of subjects. Variants will be classified as pathogenic using accepted types of variant evidence (e.g., population data, computational data, functional data, segregation data) as detailed in the American College of Medical Genetics and Genomics “ACMG Standards and Guidelines for the interpretation of sequence variants”.⁶⁰

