5 STUDY ENROLLMENT AND WITHDRAWAL

5.1 SUBJECT INCLUSION CRITERIA

To be eligible for the study, subjects must meet all of the following criteria:

1. Subjects in whom WES or WGS has already been performed, either during the CHD GENES study or, for new centers (Utah or UCSF/Gladstone), after trios in existing biobanks undergo analysis by WES or WGS during the PCGC2 grant cycle

2. Presence of deleterious mutations (damaging de novo mutations or stringently defined deleterious missense mutations) identified on sequencing (Cases) OR absence of such known deleterious mutations (Controls)
3. Males or females, age ≥ 8 years
4. Diagnosis of CHD
5. Informed consent obtained

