10.3 SAMPLE SIZE

Mean total composite achievement score will be compared for subjects with and without deleterious mutations using a two-sided, two-sample test conducted at the 0.05 level of significance. The standard deviation of achievement score is assumed to be 15 in each group. With 176 subjects with genetic mutations and 175 without mutations, we have 80% power to detect a difference in means of 4.5, or 0.3 standard deviations. If the true effect size is 0.5 standard deviations, samples of 64 subjects in each group would provide 80% power to detect a mean difference of 7.5.

Similarly, the following table provides the samples size required to attain 80% power to detect the specified effect size (i.e. standardized difference between means) between the two groups for any continuous neurodevelopmental or MRI patient level outcome at the two-sided 5% level of significance.

Effect Size	Sample Size for each group for 80% Power using Two-sample T-test
0.3	176
0.4	100
0.5	64

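### The primary genotype-outcome model has no ancestry term, and the protocol does not settle whether inherited missense variants can define a case

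*Protocol*

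**What the plan says.** **Primary model.** Section 10.2.1 compares subjects with and without deleterious mutations in a model that "will include the matching factors of site, CHD type, sex, and age category". For SES it adds that "we will also adjust for this variable in all models". This covariate set applies to primary and secondary neurodevelopmental endpoints alike.

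**Other covariates.** A further, open-ended list of examples belongs to a different set of models: "Models supporting the primary analysis will include variables that may be associated with adverse neurodevelopment as covariates". Entry there depends on a p<0.1 screen followed by stepwise selection. Ancestry, race and ethnicity are not among the examples.

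**Matching.** Section 5.3 frequency-matches controls to cases on CHD type, age category and sex, within site where possible. Some sites may recruit controls for cases enrolled elsewhere.

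**Case definition.** The Protocol Summary, section 3 (Aim 1) and section 5.1 all define cases by "damaging de novo mutations or stringently defined deleterious missense mutations". Section 2.2 has the same either/or structure and ties the missense part to meta-SVM. Section 13.4.1 describes finding cases, and clearing controls, by de novo mutations alone. Section 10.2.1 leaves the final classification to the end of the study, before database lock.

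**Available data.** Section 5.1 requires exome or genome sequencing to have been done already for every subject.

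**The concern.** A de novo variant arises anew in the child, so its presence is largely independent of ancestry. An inherited missense variant does not have that protection: how often a qualifying variant is found may differ between ancestry groups. If mean WRAT-4 scores also differ between those groups for environmental reasons that site and SES do not fully capture, part of that difference would be attributed to the mutation. The bias could go in either direction, creating an apparent effect or masking a real one.

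Site and SES are only partial stand-ins for ancestry. Site cannot remove differences within a site, and recruiting controls across sites weakens it further. The study enrols both English and Spanish speakers (section 5.2), and the outcome is reading, spelling, sentence comprehension and arithmetic. The description of the WRAT-4 norms in Appendix A lists ethnicity separately from education as an SES index. None of this shows residual confounding, but it makes it plausible.

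**Working it through.** **1. The plan's own figure.** Section 10.3 uses a "two-sided, two-sample test conducted at the 0.05 level of significance", states that "The standard deviation of achievement score is assumed to be 15 in each group", and concludes: "With 176 subjects with genetic mutations and 175 without mutations, we have 80% power to detect a difference in means of 4.5". The two-sample t-test requires 175.4, 99.1 and 63.8 per group for 0.3, 0.4 and 0.5 SD, which round up to the tabulated 176, 100 and 64. Power at 176 versus 175 is 80.0%. The sample size reproduces and is not in dispute.

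**2. Standard error of the primary contrast** (SD 15, before covariate adjustment):

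SE = 15 × √(1/176 + 1/175) = 1.60 points.

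**3. Bias from an omitted ancestry term:**

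b = (difference in ancestry share between groups) × (score difference by ancestry remaining after site and SES).

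**4. Type I error when there is no genotype effect:**

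Φ(b/SE − 1.96) + Φ(−b/SE − 1.96).

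**5. Inputs not in the protocol.** Both factors of b are assumptions: an imbalance of 5 to 10 percentage points and a residual difference of 3 to 8 points. The table treats the imbalance as applying to the whole case group.

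| Imbalance | Residual difference | Bias b | b / 4.5 | Type I error |
|---|---|---|---|---|
| 0.05 | 3 | 0.15 | 3.3% | 5.1% |
| 0.10 | 3 | 0.30 | 6.7% | 5.4% |
| 0.10 | 5 | 0.50 | 11.1% | 6.1% |
| 0.10 | 8 | 0.80 | 17.8% | 7.9% |

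**6. Dilution.** If the imbalance arises only among non-de novo missense cases, and they are a fraction f of all cases, the bias is f × b. With f = 0.25 (an assumption), the range becomes 0.25 × 0.15 = 0.04 to 0.25 × 0.80 = 0.20 points, and type I error is at most 5.2%. With f = 0 (all case variants de novo) and ancestry otherwise balanced, the bias is zero and type I error stays at 5%.

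**7. A more extreme assumption.** A 20-point imbalance with a 10-point residual difference gives b = 0.20 × 10 = 2.0 points (44% of 4.5) and type I error of 23.9% if it applies to all cases. With f = 0.25 it gives 0.5 points and 6.1%.

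**The case against.** The strongest reply is that the protocol may intend de novo variants only. Section 13.4.1 says so, and the subjects come from sequenced trios, the design needed to call de novo variants. On that reading the primary comparison is largely free of stratification. This stands as a possibility, but four other places in the protocol state an either/or definition, and the text does not say which governs.

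A reader might try to strengthen the concern with the statement in section 2.2 that variants are classified using "accepted types of variant evidence (e.g., population data, computational data, functional data, segregation data", inferring that case calls depend on population frequency and therefore on ancestry. The text does not support that. The sentence follows directly on the exclusion of clinically pathogenic copy number variants from both groups, and section 5.2 repeats it inside that exclusion. It is not tied to the calling of case missense variants.

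It is also fair to say that site and SES absorb part of any ancestry effect, that maternal education is a named candidate covariate, and that the open list would admit ancestry. The last two apply only to the supporting models, so they do not protect the primary test.

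Finally, one could argue that the covariate choice can be left to the SAP. Here, however, the protocol itself fixes the primary covariate set.

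**Conclusion.** The omission of ancestry from the primary model and the matching is established by reading. Its consequence is conditional. Population stratification is a possible confounder only if three things hold: inherited missense variants can define a case, their frequency differs by ancestry in this cohort, and WRAT-4 differs by ancestry after site and SES. The protocol leaves the first open and gives no data on the other two.

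Under the stated assumptions the bias is likely small: 0.15 to 0.8 points, or 3% to 18% of the 4.5-point target, with type I error of about 5.1% to 7.9%. It falls in proportion to the share of cases that are non-de novo missense and is near zero if there are none.

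A reader might infer that this is a known source of confounding, or that the type I error is badly inflated. Neither follows. The 24% figure needs imbalances and score differences larger than the range assumed here, applied to every case, and nothing in the protocol supports them. The change is still worth making, because it is cheap and because the final case classification is deferred, so the model should hold under whichever definition is used.

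**What to change.** 1. State whether a qualifying missense variant must be de novo, and make the Protocol Summary and sections 2.2, 3, 5.1 and 13.4.1 agree.
2. Unless it must be, add the first few ancestry principal components, computed from the sequence data already held, as fixed covariates in the primary neurodevelopmental model in section 10.2.1, outside the stepwise step.
3. In any case, include those components in the exploratory analyses of effect modification by neuro-resiliency polymorphisms. Polymorphisms are ordinarily inherited, so the de novo argument does not protect those analyses.

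**Cost.** Protocol and SAP wording, a few degrees of freedom out of about 350 subjects (176 + 175 = 351), and the work of harmonising exome and genome calls from different sources so that the components are comparable. No new data collection is needed, and the sample size calculation is unchanged.

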5.3 STRATEGIES FOR RECRUITMENT AND RETENTION

Subjects will be recruited from among those in whom WES or WGS was performed in trios gathered by the PCGC Congenital Heart Disease Genetic Network Study (CHD GENES) or from subjects at Utah or UCSF/Gladstone with trios that have undergone WES or WGS during the PCGC grant period. The latter subjects may also be recruited to participate in CHD GENES during the consent process for this study. All cases (as defined in section 5.1) deemed eligible may be recruited. Controls (as defined in section 5.1) will be recruited and will be frequency matched to cases for CHD type, age category, and sex within each site to the greatest extent possible. The matching will include four CHD type categories (i.e. single ventricle with arch obstruction, single ventricle without arch obstruction, bi-ventricle with arch

obstruction, bi-ventricle without arch obstruction), two sex categories, and three age categories (8-12, 13-17, 18+). This results in 24 unique combinations of CHD type, sex, and age category within each of the sites. A list of cases and controls will be generated for each site. To the extent possible, study personnel at the site that will have direct contact with the subjects should remain blinded as to which subjects are cases and controls. The site lists will be presented such that the blind IDs are presented in random order of cases and controls. Sites should approach each of the subjects on their lists, and subjects/families can be approached in any order. The ACC will monitor the balance of cases and controls within each site and across all sites to determine if any modifications in recruitment are necessary due to severe imbalance; if so, the ACC will work with individual sites to restore balance. Of note, some sites may be recruiting controls to match cases at other sites. Because we are using a frequency matching process in this protocol, no specific control is matched to a specific case, but rather we aim to have approximately the same number of controls as cases within each of the 24 strata.

The medical record will be reviewed or the subject's cardiologist will be contacted before initiating contact with subjects or their parent/guardian to be sure that the subject is alive.

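### The adjusted voxel-level MRI model does not force in the matching factors, screens covariates on group imbalance, and lets stepwise selection differ from voxel to voxel

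*Protocol*

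**What the plan says.** Under MRI Outcomes, Protocol section 10.2.1 gives the rule for the adjusted voxel-level comparison in one sentence. It takes variables "differentially distributed between the two groups (as identified by $p < 0.10$ in univariate analyses) as potential covariates", and then "adjusted analysis at the voxel level will be conducted using stepwise generalized linear modeling". No covariate is named as always included, and the text does not say whether selection is done once or separately at each voxel.

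The next paragraph, on MRI outcomes summarised per patient, says that the additional analyses "will include adjustment for matching factors (site, sex, CHD type and age category", and adds variables that pass the same p<0.10 screen.

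Under Neurodevelopmental Outcomes, the same section says that the primary analysis of every endpoint, primary or secondary, includes site, CHD type, sex and age category. Of socioeconomic status (SES) it says "we will also adjust for this variable in all models". Section 4.1.2 lists the brain structure and microstructure outcomes among the secondary endpoints.

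Section 5.3 says that controls are "frequency matched to cases for CHD type, age category, and sex within each site to the greatest extent possible". There are four CHD types, two sexes and three age categories, the last being 18+. It also allows that "some sites may be recruiting controls to match cases at other sites". Section 7.1.1 limits MRI to a subset at selected centers. Voxel-level results are to be controlled at a 5% false discovery rate per MRI measure.

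**The concern.** The screen asks the wrong question for design factors. Frequency matching is meant to make site, sex, CHD type and age category similar in the two groups. A rule that admits a variable only when the groups differ on it will tend to leave out the variables on which the design was built. A balanced variable that predicts the outcome still belongs in the model, because leaving it out keeps its variance in the error term. A modest imbalance that misses p<0.10 can also still bias the group contrast. The neurodevelopmental part of the same section screens its extra covariates on association with the endpoint, which is the more relevant criterion, and it does so after the matching factors are already in the model.

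The stepwise step adds a second problem. Selection depends on the outcome, and here the outcome differs by voxel. A common candidate pool does not guarantee a common final model. A map in which the group effect is adjusted for different covariates at different voxels is hard to interpret, and its p-values take no account of the selection. At stake is the adjusted voxel-level part of Aim 2.

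**Working it through.** **1. The plan's own figures.** Section 10.3 gives 176, 100 and 64 per group for 80% power at effect sizes 0.3, 0.4 and 0.5 (two-sided 5%). The normal approximation, n = 2(1.960 + 0.842)²/d², gives 175, 99 and 63 after rounding up. The t-test gives 175.4, 99.1 and 63.8, hence 176, 100 and 64. The figures reproduce. They concern patient-level outcomes, and the present point does not depend on them.

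**2. The rules side by side (section 10.2.1).**
- Patient-level MRI: matching factors included, plus screened variables.
- Primary analysis of primary and secondary endpoints: matching factors and SES included.
- Adjusted voxel-level MRI: screened variables only, then stepwise.

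The second rule stands under Neurodevelopmental Outcomes. If it reaches MRI, the third contradicts it. If it does not, no design factor is assured of a place in the voxel-level model.

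**3. How often a matched factor passes the screen.** From the documents: about 176 per group, 8 sites, 4 CHD types, 2 sexes, 3 age categories, screen at p<0.10. Assumed: equal site and sex shares; CHD shares 15/15/20/50%; age shares 40/35/25%; exact matching in the full cohort; MRI subset drawn at random. Chi-square tests, 2,000 runs (300 for the full matched cohort).

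| Sample | Each factor passes | None of the four passes |
|---|---|---|
| Full matched cohort | 0% | 100% |
| Random 50% subset | 0.2% to 1.9% | 96% |
| Random 30% subset | 1.6% to 4.6% | 87% |
| No matching at all | about 10% | 65% |

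So at least one factor becomes a candidate in about 4% (50% subset) to 13% (30% subset) of runs, and stepwise selection could still drop it.

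**4. Stepwise selection run by voxel.** Assumed: 100 per group, 6 candidate covariates each shifted 0.25 SD between groups, 1,000 independent voxels with covariate effects drawn from 0 to 0.3, no true group effect, forward entry at 0.05 or 0.10. All 2⁶ = 64 possible covariate sets occurred. The commonest covered 2.6% (entry 0.05) or 3.5% (entry 0.10) of voxels. Rejection of the true null at 0.05 was 7.8% and 6.3% with stepwise selection, against 5.8% and 5.3% with one fixed model. The Monte Carlo standard error near 5% is √(0.05 × 0.95/1000) = 0.7 percentage points, so the inflation is modest. The spread of models is partly built in, because the effects were made to vary by voxel.

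**5. What adjustment could gain.** If the factors explain a share R² of outcome variance, the effect size becomes d/√(1 − R²). Section 10.3's case of 64 per group and d = 0.5 has 80% power unadjusted. With assumed R²:
- 0.1: d = 0.527, power 84%
- 0.2: d = 0.559, power 88%
- 0.3: d = 0.598, power 92%
- 0.4: d = 0.645, power 95%

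This is a single test, not a voxel test under false discovery rate control. The protocol gives no R².

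**The case against.** Several points on the other side stand.

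- A reader might infer that the matching factors are barred from the voxel-level model. The text does not say so. Any imbalanced clinical or demographic variable can become a candidate. Matching is approximate, some controls match cases at other sites, MRI covers a subset that need not be random, and section 10.2.1 makes the final group classification only at study end. Each of these makes imbalance likelier than in the simulation.
- Section 10.2.1 compares continuous variables by t-test or Wilcoxon test, so continuous age could itself be screened. A large age difference inside the open 18+ band would tend to be caught; a modest one might not.
- The rule for all primary and secondary endpoints may be meant to cover MRI. The remedy would then be to reconcile two statements rather than to fill a gap.
- A reader might infer a loss from planned power. Section 10.3 plans no voxel-level power and uses an unadjusted t-test, so there is no planned figure to fall short of. The documents support only a possible gain of unknown size.
- A reader might add that scanners differ by site. Section 7.1.1.2 says that they will be calibrated and harmonised, which lessens the site concern without removing it.
- Selection at each voxel is an inference. An analysis plan, not seen here, could fix one covariate set.
- The false discovery rate sentence follows the description of the unadjusted tests. It is worded for voxel-level analyses in general, and is read here as covering the adjusted ones.

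These points limit certainty and severity. They do not make group imbalance a sound criterion for design factors, and they do not remove the contrast with the patient-level paragraph.

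**Conclusion.** The concern holds in this form. The stated rule for the adjusted voxel-level analysis does not assure adjustment for site, sex, CHD type or age. It differs from the patient-level MRI rule beside it, and it conflicts with the rule for primary and secondary endpoints if that rule covers MRI. Omission of the matching factors is the likely result: none of the four passes in about 87% to 96% of runs for a random 30% to 50% subset, given the assumed shares and exact matching in the full cohort. Different models at different voxels are possible because nothing prevents them, and the effect on error rates in the simulation was small.

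Severity is moderate. The primary endpoint is the WRAT-4 composite and is untouched. This is one adjusted analysis of a secondary outcome family in a subset, and section 10.2.1 leaves room for alternative MRI methods at database closure. That room does not repair the rule as written. The patient-level MRI models already carry the matching factors, and nothing here requires rewriting them.

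**What to change.** In section 10.2.1, before database lock:

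- Prespecify one model for all voxels of a given MRI measure, with mutation group, site, sex, CHD type and age. Continuous age is preferable because the 18+ band is open-ended.
- Add SES if the statement about all models is meant to include MRI.
- Delete the p<0.10 imbalance screen and the stepwise selection at voxel level.
- State that the 5% false discovery rate applies to the group term of this model.
- Say whether the rule for primary and secondary endpoints covers MRI, and make the two parts of the section agree.

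The cost is wording and a few degrees of freedom. With all 8 sites and age in three categories, the design factors use 7 + 1 + 3 + 2 = 13. The number is smaller when MRI is done at fewer centers, and linear continuous age saves one more. The four factors are the matching variables and SES is already planned for adjustment, so no new data are needed.
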